2.0 INTRODUCTION

In this initial phase open-label pilot study, we propose to enroll patients with defined inclusion/exclusion criteria at up to ten Level I/II trauma centers including Ohio State University Wexner Medical Center (Principal Site). The primary objectives are to assess the feasibility and safety of enrolling, evaluating, and treating acute cervical SCI patients with oral glyburide.

Oral glyburide is a widely used blood glucose-lowering drug that belongs to the sulfonylurea class. Blood glucose is lowered acutely by stimulating the release of insulin from the pancreas, an effect dependent upon functioning beta cells in the pancreatic islets. Oral Glyburide has been used successfully in the treatment of non-insulin-dependent diabetes mellitus (NIDDM) for more than 20 years. In treating NIDDM, the drug works by inhibiting ATP-sensitive potassium channels in pancreatic beta cells by antagonism of SUR1. This inhibition causes cell membrane depolarization, which causes voltage-dependent calcium channels to open, which in turn causes an increase in intracellular calcium in the beta cell, stimulating insulin release.

The Sur1-Trpm4 channel is selectively expressed in the central nervous system (including the spinal cord) under conditions of ischemia, hypoxia, and trauma [6, 8-10] leading to vasogenic and cytotoxic edema followed by oncotic cell death [11]. A double-blind, multicenter, randomized trial of an intravenous form of glyburide (Cirara™) in patients with large ischemic strokes likely to develop malignant cerebral edema (GAMES-RP study) identified the drug to be well-tolerated at 3 mg per day [2] with few treatment-related serious adverse events (SAEs) reported and reassuringly limited to hypoglycemia.

Neurotrauma patients, including those with spinal cord injuries, typically have elevated blood glucose levels over the first three days following their injury. For example, a large retrospective review of 528 patients with SCI [35] indicated that 53% of patients were hyperglycemic on admission (glucose concentration ≥ 126 mg/dl) and that hyperglycemia was a significant risk predictor of poor functional outcome. As such, oral glyburide administration for its potential neuroprotective effects in the SCI population appears unlikely to cause significant adverse events related to hypoglycemia and may indeed be beneficial independently given its blood glucose lowering effects.

Between August 2015 and August 2016, we screened patients with acute traumatic cervical SCIs (GOSCIP study; clinical trials NCT02524379) for potential treatment with Cirara™. Sixteen patients were screened during this period but none met the eligibility criteria. Given the ongoing enrolment difficulty with this intravenous drug within the 6 hr timeline, we have decided to amend several elements of the trial including some of the inclusion/exclusion

criteria. First, the route of administration will be changed to the oral form allowing for easier and streamlined drug administration. An extension of the window of administration to 8 hours from the time of injury will also be implemented. Several screened patients fell out of the eligibility due to this constrained time window, especially considering that Cirara™ preparation takes in the order of 1-2 hours.

The feasibility of screening, consenting, enrolling, and administering oral glyburide in the acute setting following spinal cord trauma (≤ 8 hours from injury) will be assessed at the participating centers. Further, a comprehensive assessment of all-cause AEs will be undertaken in this study for spinal cord trauma patients.

The data obtained from this pilot study should inform the design of further multicenter phase II/III clinical studies evaluating the efficacy and safety of oral glyburide in improving functional outcomes following SCI.

2.1 SCI Background

There are currently no standard of care neuro-protective strategies for the treatment of acute traumatic SCI. Methylprednisolone is no longer considered standard of care based on its dubious clinical benefit combined with its demonstrated adverse effect on immune function [3]. The sodium-channel blocker, Riluzole, was recently evaluated in a phase 1/2a trial of 36 patients by the North American Clinical Trials Network (NACTN) group [4]. While safety data appeared favorable, a larger phase 2/3 study is currently underway to assess for efficacy in improving neurologic outcomes. Other potential therapies are either at the pre-clinical or early pilot stage [33]

Progressive hemorrhagic necrosis (PHN) represents an increasingly well-characterized mechanism of secondary injury that negatively impacts neurologic outcomes. Structural failure of the integrity of intramedullary capillaries, so called ‘capillary fragmentation’ is thought to underlie this acute and dynamic secondary injury process. Animal studies modeling contusional SCIs across different laboratories have revealed a 2-2.5-fold increase in extravasated intramedullary blood within the first 12-24 hours following blunt impact trauma [5-7]. The formation of distinct microscopic

hemorrhages within the cord in turn is linked to the progressive secondary injury and neurologic deterioration following SCI.

2.2 Glyburide and Signaling Background

Glyburide (also known as Glibenclamide; 5-chloro-N-(4-[N-(cyclohexylcarbamoyl)sulfamoyl]phenethyl)-2-methoxybenzamide) is an anti-diabetic medication in a class of medications known as sulfonylureas. In treating NIDDM, the drug works by inhibiting ATP-sensitive potassium channels in pancreatic beta cells by antagonism of SUR1. This inhibition causes cell membrane depolarization, which causes voltage-dependent calcium channels to open, which in turn causes an increase in intracellular calcium in the beta cell, stimulating insulin release.

The Sur1-Trpm4 channel is selectively expressed in the central nervous system (including the spinal cord) under conditions of ischemia, hypoxia, and trauma [6, 8-10], leading to vasogenic and cytotoxic edema followed by oncotic cell death [11]. With respect to micro vascular endothelial cells, this process leads to the formation of space- occupying edema and secondary hemorrhage. Spinal cord edema and micro hemorrhage formation through this mechanism is a critical secondary injury process that progressively exacerbates mechanical compression, ischemia, and neuronal/glial cell death following trauma [12].

Numerous pharmacokinetic studies of oral glyburide have assessed single-dose administrations in normal subjects and have demonstrated significant absorption within one hour, peak drug levels at about four hours, and low but detectable levels at twenty-four hours. Mean serum levels of glyburide, as reflected by areas under the serum concentration-time curve, increase in proportion to corresponding increases in dose. Multiple-dose studies with glyburide (a widely available oral glyburide formulation) in diabetic patients demonstrate drug level concentration-time curves similar to single-dose studies, indicating no build-up of drug in tissue depots. The decrease of glyburide in the serum of normal healthy individuals is biphasic, the terminal half-life being about 10 hours [34].

In a phase 1 study of intravenous glyburide (Cirara™), the drug was administered as a bolus dose followed by a 3-day continuous infusion maintenance dose. Five groups of patients were dosed, totaling 26 patients on drug (4 dosing groups, with doses ranging from 0.4 to 10 mg/day) and 8 on placebo. There were no SAEs during the study. Two subjects (one in the 6 mg/day treatment group and one in the 10 mg/day treatment group) were discontinued from the study due to persistent hypoglycemia. The subject in the 6 mg/day treatment group who was discontinued from the study also experienced transient increases in ALT and AST levels beginning 3 days after study drug discontinuation, which returned to normal by Day 22. There were no other clinically significant drug-related AEs [1]. Based on this work, Phase 2a pilot and exploratory randomized trials were undertaken by Remedy Pharmaceuticals (GAMES-RP) wherein a total of 93 stroke patients were dosed at 3 mg/day for 3 days. There were no new safety concerns raised in these patients [36].

2.3 Rationale for Glyburide following SCI

Emerging evidence implicates the Sur1 – Trpm4 channel as the molecular precursor of PHN [6, 13-15]. Up-regulation and co-association of the regulatory and pore forming subunits of this ion channel have been demonstrated to occur in endothelial and other cells only after SCI, as demonstrated in rodents and humans [6, 16, 17]. PHN-associated secondary micro hemorrhage formation in turn is specifically associated with channel up-regulation and activation in micro vessels [6, 16, 18]. Following trauma, spinal cord edema and micro hemorrhage formation through this mechanism is a critical secondary injury process that exacerbates mechanical compression and ischemia, and contributes to neuronal/glial cell death.

Glyburide-mediated blockade of the Sur1 – Trpm4 channel in rodent models of SCI leads to minimal secondary micro hemorrhage formation and the absence of capillary fragmentation, the pathologic hallmark of PHN. Lesion volumes and hind limb locomotor functional outcome measures, measured up to 6 weeks, are significantly improved in animals treated with Glyburide shortly after the time of injury [6, 13-16]. Delayed treatment at 3 hours following SCI in rats, a more clinically-relevant time frame, also yielded significant functional benefit [19]. While the magnitude of

Glyburide-mediated neurological benefit appears to correlate with the magnitude of the initial experimental injury, significant treatment effects have been consistently demonstrated for both lesion volume and functional scores in all studies to date [14, 16, 19].

3.0 OBJECTIVES

3.1 Primary Objectives

- **Feasibility:** To assess the feasibility of running a larger phase II or III study among this population of patients where treatment must begin within a defined time frame. The number of patients who would otherwise be eligible for the study but did not receive study treatment within the 8-hour time frame will be recorded (ratio of recruited versus screened). The rate of recruitment will also be recorded.
- **Safety:** Vital signs, clinical exams, ECG, and clinical laboratory results will be carefully and continuously monitored during the course of hospitalization. Adverse events (AEs) will be assessed throughout the course of hospitalization through Day 28. In addition to presenting a summary of all AEs, where possible, a comparison of AEs occurring in study subjects vs. those occurring in matched historical controls (as captured in the NACTN registry) will be made. To facilitate this comparison, AEs will be grouped into one of 10 systems according to a modified NACTN chart [20, 21] (see appendix 1): cardiac, pulmonary, hematology, gastrointestinal/genitourinary, infections, skin, failure of stabilization, neuropsychiatric, hypoglycemia/other metabolic, and other. These AEs will be described further with respect to the specific name of the event (that is, the “type” of event; for example, for cardiac events, the type could be bradycardia or other dysrhythmia, cardiac arrest, etc.). Severity (“intensity”, as per the NACTN chart) as well as relatedness to glyburide will also be assessed. The frequency of AEs, as well as mortality (all-cause and cardiac-related), will be compared to that of a matched cohort from the NACTN registry [20, 21].

Specific outcome variables related to assessing blood glucose (BG)-related safety of glyburide are:

- Hypoglycemia (i.e. Blood Glucose (BG) < 55 mg/dL
- Symptomatic hypoglycemia i.e. hypoglycemia with investigator-identified hypoglycemic symptoms.

The following table defines which BG values should be reported as AEs:

Table 1: Blood Glucose Values and AE reporting

BG Value	Report as AE?
70-79 mg/dL	Mandatory AE reporting not required; may be reported as an AE (and coded appropriately in terms of severity) if the event meets the protocol-defined definitions.
55- 69 mg/dL	Must be reported as an AE, if confirmed by a point-of-care or lab value retest (and coded appropriately in terms of severity)
< 55 mg/dL	Must be reported as a SAE (appendix 2), if confirmed by either a point-of-care or lab value retest (and coded appropriately in terms of severity)

Specific outcome variables related to assessing cardiac-related safety of glyburide are:

- Incidence/severity of cardiac AEs and cardiac mortality
- Incidence of QTc of > 500 ms
- Mean QTc and mean change in QTc from baseline.

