1.3 Interventions and Duration

Standard of care treatment will be instituted for all patients including management of respiratory and hemodynamic parameters in a monitored setting for at least the first three days following SCI. All subjects meeting eligibility criteria will be approached as soon as possible following injury and informed consent obtained for enrollment. While all subjects will undergo standard of care computed tomography (CT) and magnetic resonance imaging (MRI) studies, only review of the CT studies will be required prior to enrollment.

As soon as feasible and if indicated, surgical intervention for spinal cord decompression and spinal stabilization will be undertaken. Safety labs and Adverse Events will be assessed through Day 14 or discharge (whichever is earlier). Serum biomarker levels will be assessed at baseline, and Days 1, 3, and 7. Adverse events will be further assessed, along with functional outcomes, at Day 28 (± 7 days), Day 42 (± 7 days), Day 84 (± 14 days), Day 182 (± 14 days), and Day 365 (± 30 days). Study participation is expected to last 365 Days ± 30 days. Adverse Event and functional outcome assessments will be undertaken by ASIA-certified study personnel.

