4.4 Study-related management (non-standard of care)

Non-standard-of-care blood work will be obtained at the following time points following the SCI:

- Pharmacokinetic Analysis: Daily, baseline through Day 3
- Biomarkers Levels: Enrollment/Baseline, 24 hours, Day 3, and Day 7

Clinical, imaging, and safety assessments will be performed throughout the study period:

- Patients will be closely monitored clinically for all AEs during the first 28 days of the study. SAEs will be monitored for the entire duration of the study. For the initial hospitalization period, the incidence of AEs will be compared where possible to that of matched controls obtained from the NACTN registry (1:3 ratio with respect to age, co-morbidities, injury level, and injury severity). The 1:3 patient matching will be undertaken by the study statistician.
- Neurological evaluation will be carried out at specific time-points up to one year following SCI to assess for changes in neurological status. The 3, 6, and 12-month ISNCSCI motor/sensory and SCIM vIII scores of the patients will also be compared where possible to that of matched controls from the literature and from the NACTN registry.

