5.10 Post-treatment follow-up

- *Post-treatment follow-up: Day 28 (± 7 days)*
 - Review unresolved AEs
 - Record additional AEs
 - ASIA Impairment Scale

- *Post-treatment Follow-up: Day 42 (± 7 days)*
 - Review unresolved AEs
 - Record additional SAEs
 - ASIA Impairment Scale
- *Post-treatment Follow-up: Day 84 (± 14 days)*
 - Review unresolved AEs
 - Record additional SAEs
 - ASIA Impairment Scale
 - Spinal Cord Independence Measure (vIII)
- *Post-treatment Follow-up: Day 182 (± 14 days) and Day 365 (± 30 days)*
 - Review unresolved AEs
 - Record additional SAEs
 - ASIA Impairment Scale
 - Spinal Cord Independence Measure (vIII)

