Death	18 (1.3)	3.7

Specifically, the following events are commonly anticipated in the SCI population in the absence of Study Drug (also see appendix 1):

Version #4

IRB Approval Date:

- Abscess
- Acute Lung Injury and Acute Respiratory Distress Syndrome
- Adjustment disorder/depression
- Autonomic dysreflexia/dysregulation
- Bradycardia
- Acute renal failure
- Anemia
- Cardiac Arrest
- Cholecystitis
- Congestive heart failure/cardiogenic pulmonary edema
- CNS infections
- Coagulopathy
- Cognitive deterioration
- Construct failure
- Deep venous thrombosis
- Depression/Adjustment disorder
- Failure of orthosis
- GI hemorrhage
- Hematuria
- Ileus
- Infectious diarrhea
- Loss of reduction
- Myocardial infarction
- Other dysrhythmia
- Pancreatitis
- Neuropathic pain
- Pulmonary embolus
- Pneumonia
- Progressive neurologic decline (motor and/or sensory)
- Psychosis
- Respiratory failure
- Seizure
- Sepsis

- Shock
- Skin complication (e.g., sacral or operative wound)
- Spinal cord edema and hemorrhage
- Thrombocytopenia
- Urinary Tract Infection
- Wound infection

In this study, AEs will be continually monitored through Day 14 or up until discharge (whichever is earlier). AEs will be further reviewed and additional AEs recorded on Day 28 (± 7 days); AEs will be followed for resolution through the end of the study. Beyond Day 28 through the end of the study, only new SAEs will be recorded.

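### The end point for recording non-serious AEs is stated inconsistently, and an in-window early Day 28 visit leaves up to 7 of the 28 days without scheduled collection

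*Combined protocol and SAP*

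**What the plan says.** Four places set Day 28 as the end for non-serious AEs. Section 3.1 (Safety) has: "Adverse events (AEs) will be assessed throughout the course of hospitalization through Day 28". Section 4.4 has: "Patients will be closely monitored clinically for all AEs during the first 28 days of the study". Footnote k of the study calendar (5.11) gives the same limit, with new SAEs and unresolved AEs followed to the end of the study. Section 6.2 closes with: "Beyond Day 28 through the end of the study, only new SAEs will be recorded".

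Two places go further. The opening text of section 6.0 has every AE recorded from enrolment until the study is complete, and requires start and end dates for each. Section 1.3 says "Adverse events will be further assessed, along with functional outcomes, at Day 28 (± 7 days"), and continues the list through Days 42, 84, 182 and 365 without limiting it to serious events.

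On how the events are gathered, section 6.2 says "AEs will be continually monitored through Day 14 or up until discharge (whichever is earlier"), followed by "AEs will be further reviewed and additional AEs recorded on Day 28 (± 7 days"). Section 5.10 matches this: the Day 28 visit records additional AEs of any kind. The next entry, "Post-treatment Follow-up: Day 42 (± 7 days"), lists a review of unresolved AEs and "Record additional SAEs".

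On use of the data, section 3.1 calls for a summary of all AEs. Sections 1.4 and 4.4 limit the comparison with registry controls to the initial hospitalization. Section 7.0 reports AE frequency without naming a time window.

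**The concern.** The AE summary is a primary safety output, and the period it covers should be the same for every patient. Here the promised period is a fixed 28 days, but the only scheduled collection of new non-serious events after Day 14 or discharge is tied to a visit that may be held a week before that period ends. The visit after it does not ask for new non-serious events. A site can follow the schedule exactly and still leave part of the period uncovered, with no deviation to flag it.

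Sites also have three possible end points to work from: Day 28, the date of the Day 28 visit, and study completion. Two sites could record different events from patients with the same history and both could point to protocol text in support. With at most 10 patients, such differences will not average out in a descriptive table.

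**Working it through.** **Inputs.** AE period: 28 days (3.1, 4.4, 6.2, footnote k). Continual monitoring: to Day 14 or discharge, whichever comes first (1.3, 6.2). Visit windows: Day 28 ± 7 and Day 42 ± 7 (5.10).

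**Step 1, visit windows.**
- Day 28 visit: 28 − 7 = 21 to 28 + 7 = 35.
- Day 42 visit: 42 − 7 = 35 to 42 + 7 = 49.

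**Step 2, days left without scheduled collection.** For a Day 28 visit held on day *v*, the uncovered days are max(0, 28 − *v*).

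| Visit day *v* | Uncovered days | Share of 28 days |
|---|---|---|
| 21 | 28 − 21 = 7 (Days 22–28) | 7/28 = 25% |
| 25 | 28 − 25 = 3 | 3/28 = 10.7% |
| 28 or later | 0 | 0% |

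For a patient monitored continually to Day 14, the 7 days are half of the remaining period: 7/(28 − 14) = 50%.

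**Step 3, whether Day 42 recovers them.** After a Day 21 visit the next visit comes 35 − 21 = 14 to 49 − 21 = 28 days later. New SAEs are recorded there. A non-serious event still present might be picked up in the review of unresolved AEs. A non-serious event that started and resolved on Days 22–28 fits neither item, so 5.10 does not ask for it.

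**Step 4, late visits.** For *v* above 28, the visit falls up to 35 − 28 = 7 days after Day 28. Section 5.10 tells the site to record additional AEs at that visit; section 6.2 admits only new SAEs beyond Day 28. If Day 28 means the calendar day, collection ends between Day 21 and Day 28 depending on the visit. If it means the visit, collection ends between Day 21 and Day 35. The shortfall in Step 2 arises under both readings.

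**Step 5, end points side by side.**

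| Place | End for new non-serious AEs |
|---|---|
| 3.1, 4.4, 6.2 (last sentence), footnote k | Day 28 |
| 5.10 | Day 28 visit, i.e. Day 21 to 35 |
| 1.3 | AEs assessed at each visit to Day 365 |
| 6.0 | Study completion (Day 365 ± 30) |

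**Step 6, which results are touched.** The registry comparison covers the initial hospitalization only. Dosing stops after 72 hours, routine glucose checks run to Hour 88 and the last scheduled ECG is at 60–72 hours (5.8), all well before Day 21. What remains exposed is the descriptive summary of all AEs in 3.1 and 7.0.

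**The case against.** The strongest reply is that the protocol already requires the missing events. Section 6.0 has all AEs recorded to study completion, 4.4 requires monitoring for all AEs over 28 days, and 1.3 lists AE assessment at Day 42. On that reading nothing is lost, and a ± 7-day visit window is ordinary practice. This stands in part: it would be too strong to say that events on Days 22–28 can never be recorded. It does not close the gap, because 6.2 and footnote k contradict 6.0 and the visit list in 5.10 follows them. Nor does the phrase about hospitalization in 3.1 settle it for patients still in hospital, since 6.2 ends continual monitoring at Day 14 for them too. Discharged patients are not covered in either case.

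A second reply is that late visits do no harm: start dates are collected, so onsets after Day 28 can be removed in analysis. That is right. A reader might infer that the window firmly extends to Day 35, but this follows only if Day 28 is taken to mean the visit, which the documents leave open.

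A third reply is that little depends on it. The only planned comparison is confined to the initial hospitalization, and the drug-specific outcomes are measured in the first days. This also stands. A reader might infer that early visits make glyburide look safer than the controls; for a discharged patient, Days 22–28 do not enter that comparison, so the documents do not support it.

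**Conclusion.** The point holds as an inconsistency in the recording period together with a limited gap in scheduled collection. The gap is at most 7 of 28 days (25%) per patient, reached when the Day 28 visit is on Day 21 and shrinking to zero by Day 28. It concerns non-serious events that start and resolve in those days, and it rests on 5.10 being followed as listed and not overridden by 6.0. For visits after Day 28, the status of onsets on Days 29–35 is undefined.

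The consequence is modest: a descriptive table in at most 10 patients whose collection period varies with visit date and with which section a site follows.

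A reader might be tempted to turn this into a number of lost events using the registry figure in 6.2, 1376/485 = 2.84 complications per patient. The documents do not support that. The figure covers the initial hospitalization, includes serious events that would still be captured (death is a row in the table), and comes with no information on how many events start after Day 14. The distribution of visit dates is also unknown.

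**What to change.** 1. Define the non-serious AE window by onset date, with onset through Day 28, independent of when the visit takes place.
2. At the Day 42 visit, for patients whose Day 28 visit was held before Day 28, add one question asking for any non-serious AE with onset through Day 28.
3. State in section 7.0 that the AE summary counts non-serious AEs with onset on or before Day 28, whatever the visit date.
4. Use the same wording in 1.3, 3.1, 4.4, 5.10, 6.0, 6.2 and footnote k. Sections 4.4 and 6.0 must be included, or the conflict with study completion will survive the change.

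The cost is one case report form question at an existing visit, one sentence in 7.0 and the wording changes. No visit is added, and the onset dates needed are already required by 6.0. The one downside is recall: an event on Day 22 asked about at a Day 42 visit held on Day 49 is 49 − 22 = 27 days old, so recall of up to about four weeks for patients seen early.
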